Effects of Botanical Microglia Modulators in Gulf War Illness

Study Protocol & Statistical Analysis Plan

NCT02909686

10/11/2022

[name], Professor, Principal Investigator
University of Alabama at Birmingham
Birmingham, AL 35294

A Placebo-Controlled, Pseudo-Randomized, Crossover Trial of Botanical Agents for Gulf War Illness: Curcumin (Curcuma longa), Boswellia (Boswellia serrata), and French Maritime Pine Bark (Pinus pinaster)

2. Materials and Methods

The full study was a pseudo-randomized, placebo-controlled, crossover clinical trial testing the effects of nine different anti-inflammatory botanical compounds on symptoms of GWI. The list of agents tested in the larger study were curcumin, boswellia, maritime pine, epimedium, fisetin, luteolin, reishi mushroom, resveratrol, and stinging nettle. Participants trialed the botanicals serially, with each participant receiving up to three botanical agents. Outcome measures were obtained daily throughout the entire duration of participation. The University of Alabama at Birmingham (UAB) Institutional Review Board first approved the study protocol (F150318011) on 30 June 2015, and the study was registered on ClinicalTrials.gov (NCT02909686) on 21 September 2016. Participants were recruited to the study through public flyers and online postings. All participants were given a written description of the study and provided written informed consent. Participants were randomized to botanicals so that each condition was completed by at least 10 individuals.

2.1. Participants

Men were considered for inclusion in the study if they were aged 37–65 and able to attend up to 11 study visits every 30 + / -3 days. Participants were required to meet Kansas GWI case definition criteria [36], with the exception that (1) participants were permitted to have a comorbid diagnosis of diabetes mellitus type 2 if controlled with medications and if having a hemoglobin A1C \leq 9% and (2) one individual with a remote history of cancer (Hodgkin's lymphoma in remission for 20 years) was included. Participants must have been present in the Persian Gulf between August 1990 and August 1991.

Exclusionary criteria included current opioid, daily anti-inflammatory, nitroglycerine, or lithium medication use; history of anaphylaxis to study botanical compounds; presence of severe depressive symptoms as indicated by a Hospital Anxiety and Depression Scale (HADS [37]) depression subscale score \geq 16; presence of a blood or clotting disorder; hypotension (under 90/60 mmHg) or history of cardiovascular disease; diagnosed rheumatologic or autoimmune disease; and acute infection (body temperature over 100.4 °F). Baseline laboratory values of erythrocyte sedimentation rate (ESR) > 40 mmHr, positive rheumatoid factor (RF), CRP > 10.0 mg/L, or positive antinuclear antibody (ANA) were also exclusionary. Participants could also not have current Posttraumatic Stress Disorder (PTSD). PTSD was initially screened with the PTSD Checklist—Military Version (PCL-M [38]), and individuals with PCL-M scores \geq 50 were given the Clinician Administered PTSD Scale (CAPS-5 [39]) for a final determination.

2.2. Botanicals

The botanical compounds were sourced from a university-approved vendor, Pure Encapsulations (Sudbury, MA, USA), prior to being sent to a compounding pharmacy for reencapsulation. Botanical compounds were re-encapsulated in size 0 or size 00 blue gelatin

capsules by Double Oak Mountain Pharmacy in Birmingham, AL. Capsules were placed in standardized QUBE Weekly (28 cavity) Cold Seal Compliance Blister packs (Pharmacy Automation Supplies, Romeoville, IL, USA).

[figure not shown]
Curcumin was obtained as Pure Encapsulation's CurcumaSorb product (SKU#: MCU1), which contains the trademarked Meriva® turmeric phytosome (Indena, S.p.A., Milan, Italy). Curcumin was administered at 1000 mg/day (lower dosage condition) and 4000 mg/day (higher dosage condition). Boswellia was obtained as Pure Encapsulation's Boswellia product (SKU# BW31) and was administered at 400 mg/day and 800 mg/day. Maritime pine bark extract was obtained as Pure Encapsulation's Pycnogenol (pine bark extract) product (SKU# PY16) which contains the trademarked Pycnogenol (Horphag Research, Hoboken, NJ, USA). Maritime pine was administered at 200 mg/day and 400 mg/day. All botanicals were administered twice per day (morning and evening), with the total daily dosage being split evenly between the morning and evening doses.

2.3. Study Protocol

All participants were assessed for initial eligibility for the study using an online prescreening questionnaire, followed by a phone interview. Individuals who met initial inclusion criteria after the online screening and phone interview were given an in-person screening at UAB's Center for Clinical and Translational Science Clinical Research Unit (CCTS CRU).

At the in-person screening visit, participants provided written informed consent as well as blood samples to test for exclusionary lab values. Participants also completed baseline study measures on a tablet device and were loaned a tablet for completion of daily symptom reporting during the study. Following the screening visit, participants reported symptoms every day (in the evening) during a one-month (30 + /- 3 days) baseline period, which served as a habituation period and a means to assess whether participants would reliably complete their daily symptom reports. Participants were allowed to continue with study participation if they completed at least 80% of baseline symptom reports.

Participants were then pseudo-randomized to receive up to three out of the nine botanical compounds, in the design presented in Figure 1. Botanical assignments were pseudo-randomized so that (1) approximately equal numbers of participants would take each botanical and (2) to ensure there were no drug interactions that contraindicated the use of the botanicals assigned to participants. There were no contraindications used for curcumin or boswellia. Individuals with prediabetes, evidence of diabetes, or diabetic medications were excluded from taking maritime pine due to its lowering effects on blood glucose [40]. Contraindications were handled by a pharmacist with no other connections to the study so that all research personnel could remain blinded to the botanical being assigned. After completion of a full protocol of three botanical assignments, participants were offered the opportunity to re-enroll into the study protocol to receive up to three more botanicals.

After the baseline period, participants returned once monthly (every 30 +/- 3 days) for up to 10 additional visits to the CCTS CRU for dispensation of their placebo or botanical capsule kits. At visits 4, 7, and 10, participants received additional blood draws to monitor liver and kidney function (sodium, potassium, chloride, bicarbonate, anion gap, glucose, blood urea nitrogen (BUN), creatinine, calcium, phosphorus, albumin, total protein, total bilirubin, direct bilirubin, indirect bilirubin, alkaline phosphatase, aspartate aminotransferase (AST), and alanine aminotransferase (ALT)). Participants were compensated for each laboratory visit.

For each botanical, participants followed the same protocol: one month (30 +/- 3 days) of placebo, one month (30 +/- 3 days) of lower-dose botanical, and one month (30 +/- 3 days) of higher-dose botanical. Study participants were blinded to both the assigned botanicals and

administration protocol (placebo, lower-dose, higher-dose). This administration order was chosen for safety reasons, i.e., adverse effects could be detected in a lower-dose condition before a higher-dose, with possibly greater adverse effects, would be administered. Research personnel were blinded to the assigned botanicals but not to the administration protocol. The study pharmacist was unblinded to both administration protocol and assigned botanicals but had no contact with study participants. Adherence to botanicals was checked at each study visit when participants returned their used blister packs. If participants had missed doses, study staff reminded them of the importance of a regular dosing schedule.

2.4. Screening Measures

The Kansas GWI case definition [36] was used to determine if participants met criteria for GWI. Exclusionary criteria for the definition included certain chronic conditions (heart disease, stroke, lupus, multiple sclerosis, cancer (other than skin cancer), melanoma, and liver disease) not associated with service in the Gulf War, as well as certain conditions that could impact participants' ability to report their symptoms (bipolar disorder or manic depression, schizophrenia, or recent hospitalization for alcohol or drug dependence, depression, or PTSD). Inclusionary criteria for the definition required that participants report presence of symptoms that began during or after service in the Gulf War. Each symptom was scored on a severity scale of 0 to 3, with 0 = none and 3 = severe. Veterans with a score of 2 (at least one moderate symptom or two mild symptoms) or greater in at least three out of six symptom domains (fatigue, pain, neurological/cognitive/mood, skin, gastrointestinal, and respiratory) met criteria for GWI.

The HADS [37] was used to screen for severe depressive symptoms. Potential participants completed the questionnaire via the Qualtrics Research Suite Online Application as part of the online prescreening process. The HADS consists of 14 items divided into two, seven-item subscales: Anxiety (HADS-A) and Depression (HADS-D). Respondents rate items on a 0 to 3 scale, with higher ratings indicating greater presence of the symptoms. Five of the 14 items are reverse scored. The total score is calculated by summing all items and ranges from 0–42. Scores of 16 or greater on the HADS-D subscale during prescreening were exclusionary for participation in the study.

To screen for severe PTSD symptoms, the PCL-M [38] was used. Potential participants completed this questionnaire via the Qualtrics Research Suite Online Application as part of the online prescreening procedures. The PCL-M corresponds to criteria according to the fourth edition of the Diagnostic and Statistical Manual of Mental Disorders (DSM-IV [41]) and consists of 17 questions referring to military experiences and symptoms of stress and trauma (e.g., repeated, disturbing memories, thoughts, or images of a stressful military experience) answered on a rating scale of 1 (not at all) to 5 (extremely). A score greater than or equal to 50 indicates a probable diagnosis of PTSD according to DSM-IV criteria [42].

If potential participants scored 50 or greater on the PCL-M during online prescreening, the past-month version of the CAPS-5 [39] was performed at the in-person screening visit by a member of the UAB Office of Psychiatric Clinical Research. The 30-item structured interview evaluates PTSD diagnostic status and symptom severity by assessing onset and duration of symptoms, levels of distress, changes in social and occupational functioning, response validity, and symptoms of the dissociative subtype of PTSD. Each CAPS-5 item is rated on frequency and intensity, which is then combined into a single severity score for that symptom. A severity rating of 2 (moderate/threshold) indicates a symptom that meets diagnostic threshold for current PTSD [43]. If a potential participant met criteria for current PTSD, they were excluded from the study.

2.5. Main Outcome Measures

The Qualtrics Research Suite Offline Application (Qualtrics, Provo, UT, USA) was used for daily symptom reporting. As part of the daily report, participants scored symptoms on a 0–100 digital visual analog scale (VAS). GWI symptom severity, the primary outcome variable of interest, was assessed by asking, "Overall, how severe have your symptoms been today?" anchored on the left by, "No symptoms at all," and on the right by, "Severe symptoms." The single-item, overall GWI severity measure was chosen as the primary outcome, because of the multisymptom and idiosyncratic nature of the condition's manifestation in affected individuals. Veterans living with GWI may primarily experience pain, fatigue, gastrointestinal distress, or any of several other common symptoms. The overall severity measure was determined to be a way to provide the most universal assessment of GWI symptom severity across participants with varying symptom presentations. Participants were instructed to use the GWI symptom severity measure to include whichever specific symptoms they attributed to GWI.

2.6. Secondary Outcome Measures

Several specific symptoms were assessed with similar one-item measures. These symptoms included pain, fatigue, cognitive dysfunction, depressed mood, dermatologic complaints, respiratory problems, and gastrointestinal distress. Of these, two (pain and fatigue) were endorsed by a sufficient number of participants to allow for statistical analysis. These two symptoms were measured with two separate 0–100 VAS items. Pain was assessed by asking, "Overall, how severe is your pain?" anchored on the left by, "No pain at all," and on the right by, "Severe pain." Fatigue was assessed by asking, "How fatigued have you felt today?" anchored on the left by, "Not fatigued at all," and on the right by, "Severely fatigued."

2.7. Statistical Analyses

Analyses were conducted using SPSS Statistics for Windows, version 24 (IBM Corp., Armonk, NY, USA). Effects of botanicals on symptom severity were tested using separate twolevel linear mixed models (LMM). LMMs are designed for nested data structures and allow for the dependence between observations typically seen with repeatedly measured variables. In this study, longitudinal outcome assessments are nested within individuals and conditions, violating the assumption of independence between observations. For each botanical, three models were built with condition (baseline, placebo, lower-dose, and higher-dose) entered as a fixed factor and symptom severity (GWI, pain, or fatigue) as the dependent variable, resulting in a total of nine models. Subject ID was used as the subject identifier, and the day in the study was the repeated measures index. A compound symmetry repeated measures covariance structure was selected, as it improved the Bayesian information criterion (BIC) and Akaike information criterion (AIC) for model performance beyond the AR (1) autoregressive covariance structure. For main analyses, daily GWI symptom severity was entered as the dependent variable. For all analyses, the outcome variable was derived by taking a mean of the last 14 days of daily symptom severity reports for each participant during each condition (placebo, lower dose, higher dose). This was consistent with the registered analysis plan, in order to allow the botanicals time to exert clinical effects. A

restricted maximum likelihood (REML) estimation approach was used. Post hoc contrasts were carried out with the least-squares differences method. Significance for all tests was set at p < 0.05.

Sample size was determined with a-priori power analyses conducted in G*Power 3 [44]. The botanical trials were powered to detect a medium effect (Cohen's d = 0.5) with 0.99 power at a p = 0.05 level of significance. Ten individuals were needed to reach 0.99 power, due to the large number of repeated outcome assessments (56 per participant, repeated measures correlation of 0.5). The trials were not powered to detect small (Cohen's d = 0.25) effects, with only 0.42 predicted power. Small effects, however, were not expected to have important clinical impacts on GWI.

A Placebo-Controlled, Pseudo-Randomized, Crossover Trial of Botanical Agents for Gulf War Illness: Resveratrol (Polygonum cuspidatum), Luteolin, and Fisetin (Rhus succedanea)

2. Materials and Methods

The three agents discussed in this report were part of a larger program of study that investigated the effects of nine anti-inflammatory botanicals on GWI symptoms. The study protocol was approved by the University of Alabama at Birmingham (UAB) Institutional Review Board on 30 June 2015 (F150318011), and this study was registered on ClinicalTrials.gov on 21 September 2016 (NCT02909686). Individuals were recruited via radio, print, and online advertisements. All participants provided written informed consent. Participants were randomized to receive up to three botanical compounds in total over the course of the study, such that each botanical was trialed by at least ten individuals. Participants recorded symptoms daily throughout the baseline, placebo, and treatment periods.

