2.7. Statistical Analyses

SPSS Statistics for Windows, version 24 (IBM Corp., Armonk, NY, USA) was used to conduct analyses. Linear mixed models (LMM) were utilized to test differences in self-reported symptom severity between the four conditions. A separate model was tested for each of the three botanicals. Subject ID was entered as the subject identifier, with all individual longitudinal data nested within-person. The participant's day in the study was entered as the index variable for repeated measures. Compound symmetry was selected as the repeated measures covariance type. The AR (1) autoregressive covariance type was also considered, but it did not improve the Akaike information criterion (AIC) or Bayesian information criterion (BIC) for model performance. The dependent variable was daily GWI symptom severity (0–100). Treatment condition (baseline,

placebo, lower-dose, and higher-dose) was entered as a fixed factor. The last 14 days of each condition were selected for analyses to permit time for clinical effects of the treatments to occur. A restricted maximum likelihood (REML) estimation approach was used. Statistical significance was set at p < 0.05 for all tests. The secondary analyses were conducted using the same approach.

We performed a-priori power analyses using G*Power 3 [43] to estimate sample size. Each of the nine botanical trials was powered to detect a medium effect (Cohen's d = 0.5) at 0.99 power with p = 0.05 threshold for significance. Given 56 repeated outcome measurements per participant (with a repeated measures correlation of 0.5), each trial required 10 individuals to obtain 0.99 power. Our studies were not powered (0.42 predicted power) to detect small effects (Cohen's d = 0.25).

A Placebo-Controlled, Pseudo-Randomized, Crossover Trial of Botanical Agents for Gulf War Illness: Reishi Mushroom (Ganoderma lucidum), Stinging Nettle (Urtica dioica), and Epimedium (Epimedium sagittatum)

2. Materials and Methods

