2.6. Statistical Analyses

All analyses were conducted in SPSS version 24 (IBM Corp., Armonk, NY, USA). For each botanical, a linear mixed model (LMM) was created to test changes in the primary outcome. LMMs were used to accommodate the repeated outcome assessments in each condition, nested in each participant. Subject ID was the repeated-measures nesting variable, the repeated-measures index was the day in the study, and the repeated measures covariance type was compound symmetry. The predictor was study condition, which could take four values (baseline, placebo, lower-dose, and higher dose botanical). The last 14 days of each condition were included in the models. The final 14 days of the baseline condition at the beginning of participation were used as the baseline for all tested botanicals. Post hoc tests were conducted using least-squares differences. A p < 0.05 was used for all tests. The same statistical approach was used to test the secondary outcomes of pain and fatigue. Nine total models are presented in this report (three botanicals tested for the outcomes of GWI severity, pain and fatigue).

If a participant did not complete the protocol, any valid data were still used in statistical tests. However, data imputation of missing values was not used, and participants were not included if they never took the assigned botanical. Therefore, we did not use a complete intent-to-treat method for analysis.

The three trials were powered to detect within-person fixed effects for study condition (baseline, placebo, lower dosage and higher dosage). Detection of a medium effect size (Cohen's d = 0.5) was targeted at a threshold of p < 0.05. With 56 repeated outcome assessments per participant, and a repeated measures correlation of 0.5, it would require 10 individuals to achieve 0.99 power for the main effect test.

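### The curcumin, boswellia and maritime pine report gives two incompatible primary outcome variables (daily scores and one 14-day mean per condition), one of them in conflict with the other two reports, and the documents do not show which was fitted

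*Combined protocol and SAP*

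**What the plan says.** The combined document holds three reports under one registration.

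- **Curcumin, boswellia and maritime pine, section 2.7.** The model has "condition (baseline, placebo, lower-dose, and higher-dose) entered as a fixed factor", and "the day in the study was the repeated measures index". The section states: "For main analyses, daily GWI symptom severity was entered as the dependent variable". The next sentence says that, for all analyses, "the outcome variable was derived by taking a mean of the last 14 days of daily symptom severity reports", one value per participant per condition. The conditions it lists are placebo, lower dose and higher dose; baseline is absent. It adds: "This was consistent with the registered analysis plan", giving as the reason that the agents need time to act. The sample-size paragraph counts 56 assessments per man.
- **Resveratrol, luteolin and fisetin, section 2.7.** "The dependent variable was daily GWI symptom severity", with the last 14 days of each condition selected.
- **Reishi, stinging nettle and epimedium, section 2.6.** The data are repeated assessments within each condition, "the repeated-measures index was the day in the study", and the last 14 days of each condition enter the model, baseline included.

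Neither of the last two reports mentions averaging. All three rest the sample size on 56 measurements, a correlation of 0.5, 10 men and power of 0.99.

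**The concern.** A condition mean has no study day, so it cannot be indexed by day. It also gives at most four values per man, not 56, and only three if the list of averaged conditions is taken literally, although the factor has four levels. The model in the curcumin report therefore cannot be run as written, and the contradiction concerns the primary outcome itself.

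The unit of analysis sets the error term and the degrees of freedom for the condition test. It also decides whether the stated power describes the test performed. A reader cannot tell which test produced the results for curcumin, boswellia and maritime pine, or whether they were tested in the same way as the other six agents.

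**Working it through.** **1. Rows and degrees of freedom, 10 men per botanical**

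- Daily scores: 4 conditions × 14 days = 56 per man, 560 rows. Error df = 560 − 10 − 3 = 547; 5% critical F(3, 547) = 2.62.
- Means: 4 per man, 40 rows. Error df = (10 − 1)(4 − 1) = 27; 5% critical F(3, 27) = 2.96.

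**2. The stated power**

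Inputs from the sample-size paragraphs: d = 0.5 or 0.25, so f = d/2 = 0.25 or 0.125; N = 10, m = 56, ρ = 0.5, α = 0.05. Within-subject F test: λ = f²Nm/(1 − ρ), df = m − 1 and (N − 1)(m − 1).

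- f = 0.25: λ = 0.0625 × 560 / 0.5 = 70, df 55/495, power 0.997 (stated 0.99).
- f = 0.125: λ = 0.015625 × 560 / 0.5 = 17.5, power 0.417 (stated 0.42).

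Both figures reproduce with 56 scores. For four means, two cases bound the answer:

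- The same f and ρ apply to the means: λ = 0.0625 × 40 / 0.5 = 5, df 3/27, power 0.39 at d = 0.5 and 0.12 at d = 0.25. Power of 0.99 at d = 0.5 would need 49 men.
- d is on the daily scale and compound symmetry holds exactly: λ stays at 70 or 17.5. Testing condition on 3 df, power exceeds 0.999 for both outcomes at d = 0.5. At d = 0.25 it is 0.95 (daily) and 0.92 (means).

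**3. How often the two outcomes give different answers**

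Both tests were applied to the same simulated data: 10 men, 4 × 14 days, complete. The daily test used compound symmetry within man. Assumed, because the documents give no variances: person SD 20, daily SD 12, and the departures in the first column. There were 2,000 to 4,000 runs per setting; ranges show repeat runs.

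| Month SD, autocorrelation | Disagree on p < 0.05, null | Disagree, 5-point change in one condition | Daily test rejects true null |
|---|---|---|---|
| 0, 0 | 0.03-0.04 | 0.04-0.06 | about 0.05 |
| 2, 0 | 0.08-0.09 | 0.12 | not computed |
| 0, 0.3 | 0.17 | 0.22 | 0.23 |
| 4, 0 | 0.28-0.30 | 0.37 | 0.34-0.35 |
| 4, 0.3 | 0.43 | 0.49 | 0.48 |

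The mean test rejected a true null in 0.04 to 0.05 of runs throughout.

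Cross-check: a month SD of 4 against a daily SD of 12 is 16/(16 + 144) = 10% of within-person variance. A separate simulation set up by variance share gave daily rejection of 0.352 at 10%, and 0.478 with autocorrelation 0.3 added. Subtracting the mean test's 0.05 leaves about 0.30 and 0.43, which are the null disagreement rates. So under the null almost every disagreement is a significant daily test beside a non-significant mean test.

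**The case against.** A reader might infer that three botanicals were in fact judged by one standard and six by another, so that results cannot be compared across the nine. The documents do not support that. Apart from the averaging sentence, the curcumin report describes daily scores: the dependent variable, the day index and the 56 assessments, on which alone the stated power reproduces. The averaging sentence may simply misdescribe a daily analysis shared by all nine.

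A reader might also infer that the six other agents depart from the registered plan. The reason attached to that sentence, time for the agents to act, explains the 14-day window rather than averaging, and the resveratrol report gives the same reason for the window alone. The reference may be only to the window, which all three reports use. The registered plan is not among the documents, so this cannot be settled here.

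The large disagreement rates come from assumed departures from compound symmetry. With complete data the condition means are identical under both outcomes and only the error term differs; under the plan's own covariance model the disagreement is small. This stands. However, the curcumin report's AIC and BIC comparison was with AR(1) alone, and compound symmetry fitting better than AR(1) does not exclude month-level variation or residual serial correlation on top of it. Complete data cannot be assumed either: the 80% diary rule applies to the baseline period only, and the reishi report uses incomplete data without imputation. Unequal day counts would make the two sets of estimates differ.

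The missing baseline in the averaging list is minor, since the four-level factor and 56 = 4 × 14 both include it.

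**Conclusion.** The contradiction is real and concerns the primary outcome, so one statement in the curcumin report must be corrected whichever model was fitted. If means were fitted, three botanicals were analysed differently from six, and the power figures of 0.99 and 0.42 do not describe their analysis. If daily scores were fitted, the averaging sentence is wrong. The text does not decide between these.

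The practical effect depends on correlation that the documents do not report. It is slight if compound symmetry is exact and the data are complete. It is substantial under the assumed month SD of 4, with or without autocorrelation of 0.3, and there the risk falls on the daily test, as false positives. Those two values are illustrations, not estimates from this trial.

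**What to change.** 1. State for all nine botanicals which outcome and unit of analysis were used, and that baseline is handled like the other three conditions.
2. Make the mean of the last 14 days in each of the four conditions the primary outcome: four rows per man, with condition rather than day as the repeated index. The curcumin report already states a 14-day mean for all analyses, and this test holds its error rate under the departures examined.
3. Re-run on existing data any agent analysed on daily scores, and report the daily-score result as a sensitivity analysis.
4. Correct the dependent-variable, index and averaging wording in the curcumin report, and align the other two reports.
5. Keep the 56-assessment calculation as the historical basis for 10 men, and restate power for the chosen outcome, saying which scale d refers to. The two cases in the working show how much that matters.

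The cost is revised wording and a re-analysis, with no new data. The downside is fewer nominal error df, and possibly less favourable p-values and lower stated power.
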